- Provide input to the investigators on the progress of the study, including periodic assessments of the data quality and timeliness, participant recruitment, accrual and retention, participant risk vs benefit, performance of the study sites, and other factors that may affect study outcomes;
- Review areas of concern regarding the performance of individual sites and provide comment to the investigators on actions to be considered regarding sites that perform unsatisfactorily;
- Consider factors external to the study when relevant information becomes available, such as scientific or therapeutic developments that may have an impact on the safety of the participants or the ethics of the study;
- Provide input to the investigators on modification of the study protocol or possible early termination of the study because of attainment of study objectives, safety concerns, low likelihood of showing a benefit of the intervention, or inadequate performance (such as enrollment and retention problems);
- If appropriate, review the interim analysis of efficacy in accordance with stopping rules which are clearly defined in the protocol and have the concurrence of the DSMB;

Statistical Analysis Plan:

Aim 1. We will assess differences between cumulative percent of goal energy and protein by study arm. We will report means and standard deviations as standard descriptive statistics. We will compare means between study arms with the Student's t tests as we expect cumulative percent of goal energy and protein to have normal distributions. Results will be considered significant at $p < 0.05$. Relationships between cumulative energy and protein delivered with clinical characteristics, mid upper arm circumference changes, and weight for age z scores will be reported by Pearson's correlation coefficient.

Aim 2. We will assess differences between FABP2, claudin 3, citrulline, lactulose/mannitol ratios, and by study arm. Descriptive plots: serum biomarker (y-variable) over time (x-variable) will be fit, with linear and smoothing splines. Plots are qualitative. Splines allow examination of possible nonlinear relationships and can be used to specify nonlinear or change-point models. We utilize one-way repeated measures ANOVA with the intestinal barrier assays as continuously measured outcomes and time (1,2,3,5, and 7 days) as explanatory variables. If the slope of the serum biomarkers is linear, then change in the slope over time will be calculated using a linear mixed effects model with an AR(1) variance-covariance structure. The variance-covariance structure allows for measurements taken closer together to be more similar than those farther apart in time, and adjusts the standard errors for this correlation. If the relationship between the serum biomarker is not linear in time, then change-point or nonlinear mixed effects models will be used. Aim Multivariable regression analysis will evaluate possible effect modification, or mediation, for non-invasive measures of intestinal epithelial barrier function. Effect modifiers are the interactions with PN group; mediators are those variables that could have a potential additive effect with the PN group. Additionally we will assess any potential confounding that might be present by assessing the change in the parameter estimate for the PN group effect. Potential modifiers, mediators, and confounders, include clinical variables, center effects, and severity of illness. We will test associations between measures of intestinal function and clinical variables, severity of illness, as well as dose and route of nutrition. With 40 subjects total, we will be able to include up to 4 possible predictors; therefore, if effect modifiers are warranted, model simplification will be necessary. If the study is stopped early the analysis plan may be modified due to small sample size.

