- a. $\text{PaO}_2/\text{FiO}_2 \leq 300$ or $\text{SpO}_2/\text{FiO}_2 \leq 260$
- b. No evidence of left ventricular systolic dysfunction
- c. Mechanically ventilated,
- 4. Require enteral tube feeding for nutrition,
- 5. Anticipate placement of central venous line within 48 hours of intubation.

Exclusion Criteria

Intent: To exclude patients with a baseline intestinal disorder (which would alter biomarkers of intestinal barrier function), or who have contraindications to premixed PN solutions or sugar permeability testing.

Patients will be excluded if at screening they have one or more of the following:

1. Premature infants and neonates < 37 weeks corrected gestational age,
2. Transfer patient from an outside facility and mechanically ventilated for >24 hours,
3. Receiving parenteral nutrition for > 24 hours,
4. Known allergy to lactulose or mannitol,
5. Pregnant,
6. Thoracic trauma, abdominal trauma, and/or active intracranial bleeding,
7. Anuric renal failure
8. Previous bowel resection and/or short gut syndrome, inflammatory bowel disease, or any patient without a functional gastrointestinal tract.
9. Cannot be enterally fed within 24 hours of admission according to the admitting physician,
10. On extracorporeal membrane oxygenation (ECMO),
11. Expected survival <24 hours or limitations to aggressive ICU care (DNR),
12. Receiving active CPR when admitted to the PICU,
13. A pre-existing bronchopleural fistula,
14. At goal enteral feeds at time of screening,
15. Previously enrolled and randomized into this protocol,
16. Actively enrolled in another clinical trial, which at the discretion of the PI would conflict with this study.

Consent and Assent

This project involves both infants and children up through the age of 16 and is categorized as 45 CFR §46.405, greater than minimal risk with potential benefit, and requires parental consent. Approach for consent must be within 24 hours of PICU admission or initiation of mechanical ventilation. Document consent approach on the Supper Screening form and whether parental consent was obtained on the SUPPER Enrollment log. Original parental consent forms are to be filed in the patient study file. Make two copies of the parental consent form, one for the family and one for bedside. Note in the patient medical record that patient was enrolled in the SUPPER Study.

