Patients ≥ 8 years of age are to be approached for assent if the patient is extubated, no longer under the influence of sedatives and analgesics, and the patient is actively receiving early or late parenteral nutrition per study. If no assent obtained because the patient is sedated and unable to participate in the assent process, document this on the assent form and keep in patient study file. If the child does not provide assent once able to cooperate with assent, the intervention is discontinued at that point. All data obtained prior to assent will be utilized. File original assent forms with original parental

consent form in the patient study file and document assent on the SUPPER Enrollment form. Make two copies of the assent form, one for the family and one for bedside.

Randomization

Randomization takes place within 48 hours of PICU admission or initiation of mechanical ventilation. Patients are blocked randomized by age and pre-existing acute or chronic malnutrition (based on admission weight for age BMI z score) to either early or late parenteral nutrition (PN) supplementation. There are 9 randomization stratifications (see table below). Randomization cards are pre-generated; random sequence was created using a random generator with atmospheric noise at random.org. BMI z-score is derived from one of two websites. If <2 years of age, use www.emmes.cpm/study/ped/resources/htwtcalc.htm; if ≥2 years of age, use www.stokes.chop.edu/web/zscore/index/php.

	1month to <3 years	3-10 years of age	11-16 years of age
BMI z score < -1 and >-2 (Low)	A1	B1	C1
BMI z score -1 to +1 (Normal)	A2	B2	C2
BMI z score > +1 and < +2 (High)	A3	B3	C3

To randomize a successfully consented patient, use age and BMI z score to determine which randomization block the patient should be in. Choose the first randomization envelope in the pack. The envelope will have a card stating the intervention arm. Record the patient's study ID, patient age, BMI z-score, name of study personnel randomizing, and date/time of randomization on the card, and staple to the SUPPER Screening Form. Document date, time and study intervention randomized on the patient's SUPPER Screening form and SUPPER Enrollment Log.

Once randomized, email the study PI the patient's study ID, age BMI z score, date and time of randomization, and assigned intervention.

Patient Kits and Supplies

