Each successfully enrolled and randomized patient will have a patient study file. This file will contain all forms for that patient. SUPPER Study Sample Kits have been provided for the collection of blood, and stool for this study. One kit is to be used per patient.

Early Parenteral Nutrition Supplementation (EPN)

Supplies, Medications, and Forms to have on hand when starting:

SUPPER Tablet with SUPPER Titration

Supplemental PN (Baxter Clinimix for patients 1 year of age and older; in-house custom PN for infants 1 month and <1 year)

SUPPER Patient Study Binder

SUPPER Sample Kit

Tape measure to perform mid upper arm circumference

Once randomized to Early Parenteral Nutrition (EPN), patients are to be started on the PN intervention within 2 hours of randomization. Patients randomized to EPN will receive enteral nutrition with supplemental PN for 168 hours. Calorie goal and titration of PN/IL are according to the SUPPER Titration Tool. **If at any point the clinical team feels that it is unsafe to continue PN, discontinue PN immediately and record this as a protocol violation. Ensure appropriate monitoring of blood glucose after abrupt discontinuation of PN.** Reducing the hourly rate of PN to achieve clinically indicated fluid restriction is also acceptable for the study protocol. All attempts should be made, and the study protocol is designed to avoid fluid overload as a result of PN. The SUPPER Titration Tool does not allow PN to exceed MIVF rates. Obtain mid upper arm circumference.

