Before initiation of EPN, collect 0 hour blood sample. This may be collected within 4 hours prior to beginning EPN to coordinate with clinical laboratory sample collection. Continue with timed sample collections as shown in the table above, using the time of EPN initiation as the starting point. All samples may be collected \pm 2 hours from target time. If patient has continuous vasoactive infusions and the infusion has been titrated within the last hour of the time of sample collection, wait at least 1 hour from time of last vasoactive infusion change. (For example, sample collection is to be drawn at 8:00am, and vasoactive infusion was titrated last at 7:30am, wait until 8:30am for sample collection). Where ever possible, match sample collection with clinical labs to reduce line access and risk of infection. For clinical variables recorded on the sample collection log use clinical data obtained within the hour prior to sample collection. (i.e. if sample collection is at 0805, record CVP from the clinical record between 0705-0805.)

While writing initial orders for EN/PN, also include orders for PINI. This includes albumin, c-reactive protein, fibrinogen, transferrin, and prealbumin. If these values are not already available pre-randomization, then obtain within 4 hours of randomization.

If the care team decides the patient does not require artificial nutrition and/or central access lines are no longer needed, PN regimen is to be discontinued.

After Initiation of EPN:

SUPPER Pre-Admit Questionnaire and SUPPER Baseline Form

Once the patient has been initiated on EPN, retrieve the SUPPER Pre-Admit Questionnaire from the patient study file. SUPPER Pre-Admit Questionnaire should be completed within 24 hours of randomization. Ideally, study personnel should sit with family and complete the questionnaire to assist the family with any questions and ensure that questionnaire is successfully completed.

Using the patient's medical record, complete the SUPPER Baseline Form. Include only information prior to time of randomization. For variables with multiple values, choose that which is closest to randomization.

SUPPER Daily Data Collection and SUPPER EN/PN Tracking Log

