The LPN intervention starts with the initiation of enteral feeds. Initiation of EN should take place within 2 hours of randomization if the patient was not already on EN. Within 2 hours of randomization, collect 0 hour blood sample and continue with timed sample collections as shown in the table below using the time of LPN initiation as the starting point. All samples may be collected \pm 2 hours from target time. Where ever possible, match sample collection with clinical labs to reduce line access and risk of infection.

While writing initial orders for EN also document PINI. This includes albumin, C - reactive protein, fibrinogen, transferrin, and prealbumin. If these values are not already available pre-randomization, then obtain within 4 hours of randomization.

	0 Hour	12 Hour	24 Hour	48 Hour	72 Hour	96 Hour	120 Hour	144 Hour	168 Hour
Blood Sample 2mLs	X	X	X	X	X	X	X	X	X
Fecal Samples (if patient has stool)	X		X	X	X	X	X	X	X
Metabolic Cart (REE)	Occurs Between 0 hour and 48 hours (DCMC Only)					Occurs Between 96 hours and 144 hours (DCMC Only)			

SUPPER Pre-Admit Questionnaire and SUPPER Baseline Form

Once LPN is initiated and 0 hour sample is collected, retrieve the SUPPER Pre-Admit Questionnaire from the patient study file. SUPPER Pre-Admit Questionnaire should be completed within 24 hours of randomization. Ideally, study personnel should sit with family and complete the questionnaire to assist the family with any questions and ensure that questionnaire is successfully completed.

Using the patient's medical record, complete the SUPPER Baseline Form. Include only information prior to time of randomization. For variables with multiple values, choose that which is closest to randomization.

SUPPER Daily Data Collection and SUPPER EN/PN Tracking Log

SUPPER Daily Data Collection forms are provided for each of the intervention days and can be found in the patient's study file. For variables with multiple values use value closest to 8:00am, unless otherwise noted. For Day 0 Daily Data Collection, only use post randomization information. These forms do not need to be completed in real time if normal bedside charting clearly provides required information, but we recommend completing them the day after they occur (ex: Day 0 completed on Day 1).

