If an adverse event occurs, it is to be noted on the SUPPER Adverse Event Log and the SUPPER Daily Data Collection form for the day the event occurred. All adverse events will be reviewed weekly by [name] to ensure study patient safety.

Report A/E and SAE per local IRB regulations as needed and required.

Data and Safety Monitoring Plan

Should study subjects have adverse events related to study interventions in Aim 1 or Aim 2 we will report these to the local and primary IRB and the Safety Officer ([name]). The DCMC study coordinator will produce Administrative Reports quarterly to describe study progress to include: accrual, subject demographics, and subject status. Reports will also describe adherence to inclusion/exclusion criteria, and protocol deviations. Safety reports will also be generated quarterly, or if enrollment exceeds expectations, at least with every 10 patients enrolled, list frequencies of adverse events, serious adverse events, safety outcomes, deaths, and disease or treatment specific events in blinded groups for review. These reports will be reviewed internally for ongoing quality control and then presented to the Safety Officer, DSMB, and IRB. The Safety Officer will review these quarterly reports to ensure good clinical care and identify any potential trends. The Safety Officer may request interim reports and analysis between meetings or prior to the scheduled interim analysis when necessary. Clinicians will be blinded to the safety monitoring data, as exposure to emerging trends may influence enrollment and care, biasing the study. This is designed as a single-blinded study so that the treating physician and investigative team are aware of group assignment in the event of electrolyte abnormalities, loss of central venous access, and related to feasibility of blinding PN. Our safety officer will also review charts for randomized subjects to ensure that no adverse events are attributable to the study intervention, this is in addition to review by the study PI.

Interim Safety Analysis

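### A central line need only be anticipated at randomization, so if parenteral nutrition (PN) waits for the line, the early arm's PN start and sample clock can slip, and hour 0 is undefined if PN never starts

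*Combined protocol and SAP*

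**What the plan says.** - **Eligibility.** Inclusion Criteria, item 5: "Anticipate placement of central venous line within 48 hours of intubation". An expectation is enough.
- **Randomization.** "Randomization takes place within 48 hours of PICU admission or initiation of mechanical ventilation". The listed steps are to find the age and BMI stratum, open the next envelope, record the result and email the study lead. None of them checks for a line.
- **Early arm, PN start.** EPN section: "patients are to be started on the PN intervention within 2 hours of randomization".
- **Early arm, link to central access.** The same section says that if artificial nutrition is not required and/or "central access lines are no longer needed, PN regimen is to be discontinued". The Data and Safety Monitoring Plan lists "loss of central venous access" among the reasons the treating team is not blinded. Neither place says what to do when a line has not yet been placed.
- **Early arm, sample clock.** Samples are timed "using the time of EPN initiation as the starting point". Of the 0-hour blood sample the manual says "This may be collected within 4 hours prior to beginning EPN", so the baseline moves with the PN start.
- **Late arm.** "The LPN intervention starts with the initiation of enteral feeds". Feeds are due within 2 h of randomization if not already running, and so is the 0-hour blood sample. Under Initiation of PN at Hour 96, late PN has a similar central-line stop rule, and it may also be forgone before hour 96. The early arm has no such provision.
- **Analysis.** The Statistical Analysis Plan compares arm means by t test (Aim 1) and models barrier markers by day (Aim 2). It names no analysis population and no fallback hour 0.

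**The concern.** A child can satisfy every eligibility and randomization rule with no central line in place, and then be allocated to an arm whose treatment is due within 2 h and appears to presuppose one. If PN waits for the line, the 2-hour rule is broken after allocation, and the clock for all early-arm samples waits as well. The same child in the late arm starts the clock with enteral feeds and gives a baseline sample within 2 h of randomization, line or no line.

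Two comparisons are exposed. In Aim 1, early-arm children with delayed or absent PN receive nutrition closer to that of the late arm, which shrinks the difference under test. In Aim 2a, a marker labelled day 1 can come from a later point in the illness in one arm than in the other. A child with no PN start has no defined sampling times at all and may drop out of the marker analysis after randomization.

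**Working it through.** The plan gives no figure for this point, so there is none to reproduce. The check sets the time windows against each other.

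**Inputs from the documents:** line expected by hour 48 after intubation (Inclusion item 5); PN due 2 h after randomization (EPN section); early-arm hour 0 = PN start (EPN section); 40 subjects in total (Statistical Analysis Plan, Aim 2).

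**Assumptions:** intubation coincides with the start of ventilation; PN starts as soon as the line is in; the line comes at the end of its expected window, which gives the maximum delay.

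**Delay.** For randomization at hour t after intubation, PN is due by t + 2. The largest overrun with the line placed inside its window is max(0, 48 - (t + 2)) = max(0, 46 - t). The 24-hour sample then falls (48 + 24) - t = 72 - t hours after randomization, against 2 + 24 = 26 h if PN starts at its deadline.

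| t (h) | PN due by (h) | Largest overrun (h) | 24-hour sample, h after randomization |
|---|---|---|---|
| 0 | 2 | 46 | 72 |
| 12 | 14 | 34 | 60 |
| 24 | 26 | 22 | 48 |
| 36 | 38 | 10 | 36 |
| 46 | 48 | 0 | 26 |

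A line placed after hour 48 gives a longer overrun, with no stated limit.

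**Comparison with the late arm.** A late-arm child whose feeds start 0 to 2 h after randomization has the 24-hour sample due at 24 to 26 h. For t = 12 the early-arm sample can fall at 60 h, a gap of 34 to 36 h. That child's baseline, drawn up to 4 h before PN, falls 48 - 4 - 12 = 32 h to 48 - 12 = 36 h after randomization, against at most 2 h in the late arm.

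**Numbers affected.** These cannot be derived from the documents. As illustration, assume 20 children per arm and a probability p that an early-arm child never gets a line. The expected number is 20p and the chance of at least one is 1 - (1 - p)^20:
- p = 5%: 1 child, 64%
- p = 10%: 2 children, 88%
- p = 20%: 4 children, 99%

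**Dilution.** If a share f of the early arm never receives PN and on average has the late-arm outcome, the arm difference is multiplied by 1 - f. The plan states no effect size. With 20 per arm, two-sided 0.05 and a normal approximation, 80% power needs a standardized difference of (1.960 + 0.842) × √(2/20) = 0.886. Power then falls to 76% at f = 5%, 71% at 10% and 61% at 20%. This is illustration only.

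**The case against.** The strongest reply is that the premise is inferred. No sentence requires study PN to go through a central line or bars another route; the link rests on inclusion item 5, the stop rules and one remark about blinding. That stands, and it is why every figure above is conditional on PN waiting for the line. It does not dispose of the point: if another route is acceptable, the manual does not say so.

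Second, the windows can be met together. The consent approach closes at 24 h and randomization at 48 h, so a site may consent early and hold the envelope until the line is in. That is true, but nothing tells sites to do so, and practice may differ between them.

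Third, missed PN and missed blood samples are logged as protocol deviations, and blood may be drawn from any indwelling clinical catheter. Both are correct. Neither supplies an hour 0 or says how such a child is analysed.

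Some stronger readings are tempting but not supported:
- *Early-arm children without a line cannot enter the sample clock.* A late line delays the clock; only a child who never starts PN has none.
- *All failure to deliver PN falls on the early arm.* Late-arm PN from hour 96 is also tied to central lines. Only the shifted or undefined hour 0 is particular to the early arm.
- *The delay removes a fixed share of the 96 h in which the arms differ.* That mixes two clocks. Early-arm hours run from the PN start, and the manual does not say that a late start shortens the 168 h course.
- *Line placement tracks severity of illness, so the loss is informative.* This is plausible, but no passage supports it.
- *Some children are known to be affected.* The documents allow it; they do not show it.

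**Conclusion.** The point holds as a gap between eligibility, randomization and the early-arm schedule. As written, the plan permits an early-arm child to be allocated before a line is in place. If PN waits for the line, its start can fall up to 46 - t hours after the 2-hour deadline, hour 0 shifts by the same amount, and hour 0 does not exist if PN never starts. The late arm's clock has no such dependence.

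The size per child follows from the manual's own windows, given that condition and a line placed at the end of its expected window. The number of children, the loss of power and any bias cannot be computed from the documents; the shares, the 20 per arm and the effect size used above are assumptions. With 40 subjects in total, a few such children would matter, and the remedy is cheap. The sponsor should make the change, but the point does not show that the trial fails.

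**What to change.** 1. Reconcile Inclusion item 5, Randomization and the EPN section, and state what access study PN uses. Which access rule applies is for the sponsor to decide.
2. Keep item 5 for screening and consent. Add a check immediately before the envelope is opened: the access used for study PN is in place. If it is not in place by the end of the existing 48-hour window, log the child as not randomized. Any waiting or exclusion then happens before allocation and applies to both arms alike.
3. Count sample hours from randomization in both arms, so that hour 0 never depends on PN starting. This also removes the ambiguity for late-arm children whose feeds began before randomization.
4. State in the Statistical Analysis Plan that all randomized children are analysed by assigned arm, and report by arm the time from randomization to PN and the number who never started it.

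**Cost.** One line in the randomization checklist, a revised sample-timing rule and a sentence or two in the analysis plan; no new procedure. Some children will be randomized later in the window. Because the manual aims for full enteral feeds within 48 h of starting them, feeds may by then be further advanced and the PN contrast smaller. A few consented children will not be randomized. For a child whose line comes late, PN itself starts no sooner; what changes is that the wait comes before allocation.

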Due to frequent collection of study labs, it is recommended to speak with bedside nurse at these times to gather information about possible adverse events or signs of feeding intolerance. Supper study labs may be delayed by 1-2 hours, if necessary, to ensure that blood collection occurs at a time when vasoactive infusions have not been titrated for 1 hour. Data on the daily sample collection forms (vital signs and clinical data) are to be collected as the most recent vital sign in the hour PRIOR to blood sample collection.

Using nutrition charting and tracking of in/out fluids, complete a SUPPER EN/PN Tracking Log for each study day.

Metabolic Cart Testing

Within the first 48 hours of the intervention, the patient's Resting Energy Expenditure (REE) is to be tested using the site's available metabolic cart. Print at least two copies of the REE results; one for the patient study file and one for the patient's medical record. Attending physician should be updated on REE results. Record REE results on the SUPPER Sample log and file in the patient's study file. Repeat REE between Hour 96 and 144 of the intervention.

Prescribed kcal/day from the REE maybe different than the calculated kcal/day goal from the SUPPER Titration. If it is different, enter the new Measured REE kcal/day in the space provided. The SUPPER Titration sheet will utilize this new goal and adjust EN rates accordingly.

At Hour 96 record PINI. This includes albumin, C - reactive protein, fibrinogen, transferrin, and prealbumin.

Initiation of PN at Hour 96

At hour 96, late supplemental PN is initiated if the patient is not meeting 80% of calorie goal on EN feeds alone. Choice of PN is based on patient age. If patient is 1 year of age or older, patients will receive Baxter Clinimix E 5/15. Patients between 1 month of age and 1 year of age will receive in-house custom PN. Enter PN/EN doses into SUPPER Titration, and start tracking PN on the PN/EN Hourly Log with first PN entry under the hour PN is initiated. The bedside nurse will titrate PN to maintain calorie goal and protein every 4 hours with the aid of the SUPPER Titration Sheet. As patient tolerates increased EN, PN is decreased.

If the care team decides the patient does not require artificial nutrition and/or central access lines are no longer needed, PN regiment is to be discontinued, or foregone if before 96 hours.

Discharge and Follow Up

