Prior to patient PICU discharge, complete the SUPPER Contact Form with the parent/guardian that provided consent for this study. This form will be used for the 28 Day Vitals check if patient is not in the hospital or deceased.

There are 5 key sections to the SUPPER Discharge Form, Extubation, PICU Discharge, Hospital Discharge, Early Cessation, and 28 Day Vitals and Patient Death. Complete each of these sections as they occur.

To assess 28 Day Vitals, first check to see if the patient is still hospitalized or if the patient died while hospitalized. If patient is not hospitalized, use the SUPPER Contact Form to contact the patient's parents/guardians. Three attempts should be made to contact the parents/guardians. If the third attempt is unsuccessful, attempt to contact the patient's primary care physician. If the patient has not been seen by the primary care physician since hospitalization, assess vital status from county death records. If you can successful contact either the patient's parents/guardians or primary care physician obtain information on whether the patient's condition is better, the same, or worse from condition at

discharge. Also obtain information on whether the patient was readmitted to the hospital on or before 28 Days.

Subject Withdrawal

Subjects may withdraw from the study at any time. Should the patient or the patient's parents/guardians wish to withdraw, note the date, time, and reason for withdrawal on the SUPPER Discharge Form. If the patient is receiving supplemental PN when they wish to withdraw from the study, review the risks associated with abrupt discontinuation of PN, and advise that the patient will require blood sugar monitored 2-3 times over a 24 hour period to ensure they do not develop hypoglycemia. Ask parents/guardians if we may continue to collect information from the medical record without continuing any study procedures for outcome analysis. If they gave permission to bank samples for future research, ensure this has not changed.

Data Collection and Entry into REDCap

Prior to starting the study, sites will provide a written plan on how and from what system data is obtained. This is to assist with consistency of source of information, and to provide a guide for data monitoring. For instance, if vitals and medications are found in different applications of the medical record system, it should be noted where source documentation is obtained.

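### Assent is tied to receiving study PN, so before hour 96 only early-arm children can be asked and stopped, and late-arm children who never start PN are not asked at all

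*Combined protocol and SAP*

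**What the plan says.** Consent and Assent sets three conditions that must hold together before a child is asked. The first is age and extubation: "Patients ≥ 8 years of age are to be approached for assent if the patient is extubated". The second is that the child is "no longer under the influence of sedatives and analgesics". The third is that "the patient is actively receiving early or late parenteral nutrition per study". On refusal, "If the child does not provide assent once able to cooperate with assent, the intervention is discontinued at that point". On data, the section says "All data obtained prior to assent will be utilized" and nothing about data after that moment.

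The third condition is met at different times in the two arms. Under Early Parenteral Nutrition Supplementation, "patients are to be started on the PN intervention within 2 hours of randomization", and PN alongside EN is planned for 168 hours. For the late arm, the section on starting PN gives this rule: "At hour 96, late supplemental PN is initiated if the patient is not meeting 80% of calorie goal on EN feeds alone". The late-arm section plans 72 hours of PN from that point. It is not started if, before hour 96, the care team judges that artificial nutrition or central access is no longer needed.

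Both arms have the same blood and stool schedule to hour 168. Sample Collection limits blood draws to catheters already in place for clinical care.

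Subject Withdrawal lets subjects leave at any time. It covers a wish to withdraw by the patient as well as by the parents, and then instructs staff: "Ask parents/guardians if we may continue to collect information from the medical record".

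**The concern.** A trigger for assent should not depend on the randomized arm. Here it does, because one of its three conditions is receipt of the treatment whose timing is randomized. Two things follow.

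First, a child's refusal stops the intervention, and before hour 96 that can happen only in the early arm. It can also happen only in children who have recovered enough to be extubated and awake. Aim 1 compares cumulative percent of goal energy and protein, and Aim 2 follows barrier markers to day 7, so both depend on what happens across the week. Stopping that is open to one arm and linked to recovery is unwelcome in a randomized comparison, particularly a small one: the Aim 2 analysis plan works from 40 subjects in total.

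Second, a late-arm child of 8 or over who is awake and able to take part may remain under study sampling without being asked, in a study that the manual classes as greater than minimal risk.

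**Working it through.** No power or error-rate calculation applies. The check sets the stated time windows against the three assent conditions.

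**The plan's own figure.** End of intervention minus earliest late-arm PN start: 168 − 96 = 72 hours. This agrees with the 72 hours in the late-arm section.

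**When the PN condition can be met, by arm**

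| Period | Early arm | Late arm |
|---|---|---|
| Hour 0 to 96 | Yes, while PN is running | No |
| Hour 96 to 168, below 80% of goal at hour 96 | Yes, while PN is running | Yes, while PN is running |
| Hour 96 to 168, at or above 80% of goal, or PN not started | Yes, while PN is running | No |
| Planned maximum | 168 hours | 72 hours, or 0 if PN is never started |

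The ratio of the two planned maxima is 168 / 72 = 2.33. These are ceilings, not expected windows:

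- Every child is ventilated at entry, so no child meets the extubation condition at hour 0.
- Early-arm PN is reduced as EN advances, with full enteral feeds aimed for within 48 hours of starting EN.
- In both arms, PN ends if artificial nutrition or central access is judged unnecessary.

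**A worked case.** Take two children aged 8 or over, one per arm, both extubated and unsedated at hour 60.

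- *Early arm, still on PN.* All three conditions hold and the child is approached. On refusal the intervention ends with 168 − 60 = 108 planned hours remaining.
- *Late arm, on EN alone.* The third condition fails. The earliest it can be met is 96 − 60 = 36 hours later. If EN is at 80% of goal or more at hour 96, or PN is not started for another reason, it is never met. Blood draws are still scheduled at hours 72, 96, 120, 144 and 168: 5 × 2 mL = 10 mL, plus stool at the same times. The blood draws happen only while a clinical catheter remains.

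**Who is affected.** Only children aged 8 or over: the 11–16 stratum and part of the 3–10 stratum. The manual gives no expected number for either, and no expected rate of early extubation or of refusal.

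**Analysis.** The Statistical Analysis Plan compares by study arm but does not say how a child stopped for non-assent is handled.

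**The case against.** The strongest reply is that the arms are themselves named early and late parenteral nutrition, and the late-arm section says that intervention begins with enteral feeds. The assent condition could therefore mean being on either assigned strategy, and the asymmetry would disappear. This reading is possible but does not fit the words about actively receiving PN, and the hour-96 section uses late supplemental PN for the infusion itself. If the broader meaning was intended, the text needs to say so.

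A second reply is that any child may withdraw at any time in either arm. That is true, but it relies on the child or family raising it; it is not an approach for assent. The assent forms are not in the copy reviewed and may say more, but the manual is what staff follow.

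Three stronger readings are tempting, and the documents do not support them:

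- *That data after dissent are discarded.* The section says earlier data will be used. It is silent on later data and does not exclude them.
- *That continued chart collection is sought only when a parent withdraws.* Subject Withdrawal covers the patient's own wish too. What is missing is a link from dissent to that route.
- *That the true imbalance in approachable time is well above 2.33 to 1, because some late-arm children never need PN.* Discounting the late arm alone is one-sided. Children who feed well enterally would also be on little or no PN in the early arm, and a child awake at hour 60 may already be off it.

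**Conclusion.** The point stands as a defect in the assent procedure. On its plain wording, the trigger depends on arm: before hour 96 only early-arm children can be asked and stopped, and late-arm children who never start PN are not asked at any time. Assent-driven stopping therefore depends on both arm and recovery.

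Its effect on the trial's results cannot be sized. A child must be aged 8 or over, extubated, unsedated, still on PN and unwilling to continue, and the documents give no figure for how often these coincide. A reader might infer a material bias in the Aim 1 or Aim 2 comparison; the documents support only the possibility. The planned maxima of 168 and 72 hours are the only firm numbers, and real windows are shorter in both arms. The conclusion assumes that the PN condition refers to the infusion and not to the assigned strategy. The change is worth making because it is cheap, removes an arm-dependent route to stopping, and means that late-arm children able to assent are asked.

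**What to change.** Amend Consent and Assent so that every child aged 8 or over, in both arms, is approached once extubated and able to take part, for as long as any study procedure remains, sampling included, whether or not PN is running.

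Link dissent explicitly to Subject Withdrawal, so that permission to keep collecting chart-based outcomes is sought from the parents. State what a refusal means for further study samples, which the assent section leaves open. Add a sentence to the Statistical Analysis Plan keeping children stopped for non-assent in their randomized arm, and report their number by arm with the time of stopping.

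The cost is a short amendment to the manual and, where affected, the assent form. There will be a few more assent conversations, and possibly a few more refusals, in the late arm.
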